2.5.3. Trial Completion

A study exit form must be completed when:

- The subject withdraws from the clinical trial
- The subject is considered lost-to-follow-up per the above definition
- The subject did not receive the index treatment due to disqualifying factors
- The investigator withdraws the subject
- Subject receives additional treatment for index thumb OA within 6 months.
- More than one cross-over of study treatment in index hand
- Subject receives invasive treatment for thumb OA other than one of the study treatments in index hand
- Upon trial follow-up completion (6-months follow-up time point has been reached)
- The subject has died

2.6. Description of Assessments and CRFs

All data to be collected is described below.

2.6.1. Demographics

Demographic information collected will include gender, age, height and weight.

2.6.2. Medical History

Information regarding systemic inflammatory conditions, currently active malignancy, pregnancy, lactation status, leukemia and current chemotherapeutic drug use will be obtained.

2.6.3. Medication Use

Information regarding the subject's medication use for treatment of thumb OA will be collected.

2.6.4. Patient Reported Outcome Measures

- Disabilities of the Arm, Shoulder and Hand (DASH):

The DASH questionnaire is a tool already validated and used for the assessment of the patient's disability related to the pathology of the upper extremity (in this case of the hand) in the control of normal actions of daily life. The questionnaire consists of 38 questions, for a possible score ranging from the value 0 to the value 100. A higher score indicates the greater severity of the degree of disability felt by the patient in relation to the pathology.

- Visual Analogic Scale: The VAS is a validated measure of knee pain. The NRS is an 11-point Likert type scale anchored by 0 "no pain" and 10 "worst possible pain". Subjects rate their average pain over the last 48 hours.

- Grip strength test e tip pinch strength test:

The Grip Strength Test and the Tip Pinch Strength Test are designed to measure the maximum isometric force exerted by the muscles responsible for flexion of the metatarsals and phalanges, flexion of the fingers and adduction of the thumb. The tests are carried out by means of a dynamometer to record the changes in force in the gripping and gripper movements.

- Kapandji Score:

The Kapandji score assesses the patient's ability to oppose the thumb, assigning a score based on the point of the hand they can touch.

- Nine-Hole Peg Test:

The Nine-Hole Peg Test is a test that uses 9 pegs and a board with 9 holes: the patient is asked to place the pegs one by one in the holes and then remove them and put them back in the container. The score is given by the time in seconds that the patient takes to perform the maneuver.

2.6.5. Imaging Assessments

2.6.5.1. Trapeziometacarpal joint Radiograph

A standing posterior-anterior (PA) and lateral fixed radiographs of the index hand are acquired and

classified using the E-L grade by an expert radiologist.

2.6.5.2. Magnetic Resonance Imaging

MRI will be used to assess baseline comorbidities and will not be used to determine eligibility. Key comorbidities, including but not limited to subchondral fractures, subchondral bone cysts, micro fractures, ligament tears, and bone marrow lesions will be recorded.

2.6.6. Additional Case Report Forms

2.6.6.1. Adverse Events

AE forms will document a description of the AE, onset date and duration, severity, seriousness, treatment, and relatedness. The form will also document whether the event was anticipated or unanticipated.

2.6.6.2. Study Exit Form

This form will document termination of each subject's study participation and capture the reason for study exit.

2.6.6.3. Protocol Deviation Form

This form will document deviations from the study protocol.

3. Adverse Event reporting and management

All AEs reported to or identified by investigative center personnel occurring during the study period and after the treatment procedure will be documented. AEs will have the onset and resolution date(s) listed (when known), will have their management and outcome documented (where feasible), and will be assessed for severity, relatedness, and whether they were anticipated. SAEs will be described in a narrative in the final study report.

Anticipated AEs associated with the injection procedure include worsening of hand pain and/or function, effusion, and infection.

3.1. Definitions

Adverse Event

An AE is any untoward medical occurrence, unintended disease or injury or any untoward clinical signs (including an abnormal laboratory finding) in subjects, users or other persons whether or not related to the investigational medical device.

NOTE 1: This definition includes events related to the investigational device or the comparator.

NOTE 2: This definition includes events related to the procedures involved.

NOTE 3: For users or other persons, this definition is restricted to events related to investigational

medical devices.

Exceptions include events that are pre-existing (prior to injection) and have not changed in severity or intensity. If a pre-existing complication or event changes in severity or intensity then it should be reported as an AE.

Serious Adverse Event

A SAE is an AE that:

- a) leads to a death,
- b) leads to a serious deterioration in health of the subject, that either resulted in:
 - Life-threatening illness or injury, or
 - Permanent impairment of a body structure or a body function, or
 - In-patient hospitalization² or prolongation of existing hospitalization, or
 - Medical or surgical intervention to prevent life threatening illness or injury or permanent impairment to a body structure or a body function,

NOTE 1: Planned hospitalization for a pre-existing condition, or a procedure required by the clinical study protocol (without a serious deterioration in health) is not considered a SAE

Adverse Device Effect

AE related to the use of an investigational medical device.

NOTE 1: This includes any AE resulting from insufficiencies or inadequacies in the instructions for use, the deployment, the implantation, the installation, the operation, or any malfunction of the investigational medical device.

NOTE 2: This includes any event that is a result of a use error or intentional abnormal use of the investigational medical device.

The following are identified as possible examples of ADEs:

- Injection site reaction – swelling, redness, burning, itching at the injection site – to a degree that is atypical of an intra-articular aspiration and injection procedure
- Hand arthralgia – severe pain in the thumb joint
- Thumb joint ache – to suffer dull, continued pain
- Thumb joint inflammation – a localized protective reaction of tissue to irritation, injury, or infection—characterized by pain, redness, swelling, and sometimes loss of function

²Any admission over 24 hours will be considered as an in-patient hospitalization

- Thumb joint effusion – the escape of fluid from the blood vessels or lymphatics into the trapezio-metacarpal joint
- Trapezio-metacarpal arthrosis – degenerative disease of the thumb joint – beyond what is considered normal OA progression

Serious Adverse Device Effect

A Serious Adverse Device Effect (SADE) is an ADE that has resulted in any of the consequences characteristic of a SAE.

Unanticipated Serious Adverse Device Effect

An Unanticipated Serious Adverse Device Effect (USADE) is a SADE which by its nature, incidence, severity or outcome has not been identified in the current version of the risk analysis report.

NOTE: Anticipated SADE (ASADE): an effect which by its nature, incidence, severity or outcome has been previously identified in the risk analysis report

Device Deficiency

Inadequacy of an investigational medical device related to its identity, quality, durability, reliability, safety or performance. This may include malfunctions, use error, or inadequacy in the information supplied by the manufacturer.

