2.4.2. Randomization

Randomization will occur through a module in the CRF. Once randomization is complete and a treatment arm is assigned.

Eligible subjects will be randomized in a 1:1 ratio to one of following two treatment arms:

- Subject device: OOT plus thumb splint
- Comparator device: thumb splint

Details regarding randomization can be found in Section 4.4.1.

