- the discontinuation of medical device application or the reduction of the level of activation/exposure - when clinically feasible - and reintroduction of its use (or increase of the level of activation/exposure), do not impact on the event;
- the event involves a body-site or an organ not expected to be affected by the device or procedure;
- the event can be attributed to another cause (e.g. an underlying or concurrent illness/clinical condition, an effect of another device, drug, treatment or other risk factors);
- the event does not depend on a false result given by the investigational device used for diagnosis, when applicable;
- harms to the subject are not clearly due to use error;

In order to establish the non-relatedness, not all the criteria listed above might be met at the same time, depending on the type of device/procedures and the event.

2. Unlikely: the relationship with the use of the device seems not relevant and/or the event can be reasonably explained by another cause, but additional information may need to be obtained.
3. Possible: the relationship with the use of the investigational device is weak but cannot be ruled out completely. Alternative causes are also possible (e.g. an underlying or concurrent illness/clinical condition or/and an effect of another device, drug or treatment). Cases where relatedness cannot be assessed or no information has been obtained should also be classified as 'possible'.
4. Probable: the relationship with the use of the investigational device seems relevant and/or the event cannot be reasonably explained by another cause, but additional information may need to be obtained.
5. Related: the event is associated with the investigational device beyond reasonable doubt when:
the event is a known side effect of the product category the device belongs to or of similar devices and procedures;
 - the event has a temporal relationship with investigational device use/application or procedures;
 - the event involves a body-site or organ that
 - the investigational device or procedures are applied to;
 - the investigational device or procedures have an effect on;
 - the event follows a known response pattern to the medical device (if the response pattern is previously known);
 - the discontinuation of medical device application (or reduction of the level of activation/exposure) and reintroduction of its use (or increase of the level of activation/exposure), impact on the serious event (when clinically feasible);

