4.1. Potential Risks to Study Subjects

Subjects in this study are exposed to potential risks associated with aspiration of joint fluid, and solution injection into the thumb joint. These include pain, bleeding, bruising, infection, deep venous thrombosis, scar tissue formation, thrombotic complications and nerve damage. These risks are not unique to this study and may occur with any aspiration, or joint injection procedure. The use of joint splinting could create discomfort, venous or lymphatic stasis present in the relevant hand.

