7.5. Safety Analysis

The safety profile of OOT will be characterized by summarizing AEs, which will be standardized using the Medical Dictionary for Regulatory Activities. Characterization will include narratives of all SAEs and descriptive statistics including AE incidence overall and per subject, AE severity, AE device relatedness, and AE onset for each treatment group. AEs will also be used to characterize the safety of a repeat OOT injection. Results will be tabulated by treatment group.

8. Study monitoring and quality control

The investigational sites will be monitored to ensure compliance with the trial protocol, adherence to applicable regulations, and accuracy of trial data. Monitoring visits will be conducted primarily to ensure that the safety and wellbeing of the subjects is preserved. Monitoring visits will also be used to verify that trial data submitted on case report forms are complete and accurate with respect to the subject medical records and to verify device accountability. The principal investigator, his/her delegate(s) and the study coordinator(s) shall be accessible during monitoring. Accessibility is of particular importance for reviewing data in the CRF. Site personnel will complete CRFs following each subject visit. Trial data submitted will be reviewed against patient charts and other sources containing original patient records. As needed, intermittent monitoring visits will be conducted to compare data entered into the database to a selected sample of the subjects' source documents. Monitoring efforts will be expanded where the sample suggests irregularities.

Prior to the first site activation, a Monitoring Plan will be established outlining the activities above, as well as management of trial materials supplied to sites.

9. Ethical and legal considerations

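### Undefined device terms and a single relatedness grade allow splint harms to be classified inconsistently between arms and keep the relatedness table from isolating OOT events

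*Combined protocol and SAP*

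**What the plan says.** Section 2.4.2 labels the arms "Subject device: OOT plus thumb splint" and "Comparator device: thumb splint". Section 2.4.5 gives every patient two splints, a day and a night one, to be used for 2 months.

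Section 3.1 defines an AE broadly: "NOTE 1: This definition includes events related to the investigational device or the comparator". A second note extends the definition to the procedures involved. An ADE is narrower: "AE related to the use of an investigational medical device". The serious ADE (SADE) and the unanticipated serious ADE (USADE) are built on the ADE, so they carry the same limit.

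Section 3.2 has the investigator give each AE one grade, on a five-point scale, for its relationship to the 'study device'. One ground for grading an event 'not related' is that it can be put down to another cause, for example "an effect of another device, drug, treatment or other risk factors".

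Section 4.1 foresees splint harm: "The use of joint splinting could create discomfort, venous or lymphatic stasis present in the relevant hand". The list in section 3 concerns the injection: "Anticipated AEs associated with the injection procedure include worsening of hand pain and/or function, effusion, and infection".

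Section 7.5 sets out to describe the safety of OOT and will report, among other things, "AE severity, AE device relatedness, and AE onset for each treatment group".

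**The concern.** Three terms are in use: 'subject device' (2.4.2), 'investigational medical device' (3.1) and 'study device' (3.2). None is defined by reference to the others. The splint is the one item that both arms share, and it changes label between arms. An investigator who sees splint-related stasis has no rule saying whether it is device-related, or whether the answer depends on the patient's arm.

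The relatedness table in section 7.5 is at stake, together with any ADE, SADE or USADE classification. If investigators apply different readings, differences in that table may reflect labelling. Even if all apply the same reading, one grade per event does not show which component of the combined treatment was held responsible.

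**Working it through.** The plan states no figure on this point and no arithmetic decides it. The check sets the rules side by side.

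**Scope of each rule**

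| Rule | Investigational device | Comparator | Procedures |
|---|---|---|---|
| AE (3.1) | yes | yes, by note | yes, by note |
| ADE, hence SADE and USADE (3.1) | yes | not named | not named |
| Relatedness grade 1, not related (3.2) | 'the device' | not named | yes |
| Grades 2 to 4 (3.2) | 'the device' or the investigational device | not named | not named |
| Grade 5, related (3.2) | yes, in its lead line | not named | yes, in some criteria |

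The comparator appears in the AE definition and then drops out. Procedures appear only at the two ends of the relatedness scale.

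**One splint injury under each reading of the device term**

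Suppose k such injuries occur in each arm, so that there is no true difference.

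- Reading A: the investigational device is the subject device of 2.4.2, OOT plus splint. ADE count: k in the combined arm and 0 in the splint arm. In the splint arm, the other-device criterion could also be used to support 'not related'.
- Reading B: the device is OOT alone. Count: 0 and 0. Splint harm is attributed to a device in neither arm, and the splint arm can have no true device-related event.
- Reading C: the device is any device used in the trial, or splinting counts as a procedure when relatedness is graded. Count of device-related events: k and k.

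Only Reading A creates a difference between arms. The documents do not choose among the three.

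**Can the table isolate OOT?**

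Under A or C, a 'related' grade in the combined arm may refer to the gas, to the aspiration and injection, or to the splint. The form holds one grade, so the three cannot be separated in the table. Under B, splint harm is excluded, but the grade still does not separate the gas from the injection procedure, and splint harm is recorded against no device.

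**What does not depend on relatedness**

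The other section 7.5 summaries (AE incidence overall and per subject, severity, and onset by group) use every AE whatever its grade. Since both arms wear splints, those contrasts still compare OOT and its injection with no injection.

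**The case against.** The strongest reply is that the documents never equate the subject device with the investigational device, so the step that produces an arm difference is an inference. The ADE examples in 3.1 describe the injection site or the joint and none is specific to a splint, and 7.5 is about OOT. Both fit Reading B, which treats the arms alike. Section 2.4.5 is headed as a splinting procedure and applies to every patient, so the references to procedures in grades 1 and 5 would let a splint injury be graded related in either arm. The other-device wording is one example within one criterion, and 3.2 says that not all criteria need be met. Each AE also carries a description from which the component might be recovered.

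Much of this stands. A reader might infer that the protocol does classify the same injury differently by arm and that the groups therefore cannot be compared on safety. The documents do not support that: it follows under one reading of three, and the overall AE summaries are untouched. A reader might also infer a risk of a false-positive safety finding. Section 7.5 plans descriptive statistics only and the documents give no splint-event rate, so a significance test on assumed counts would say nothing about this plan. Nor is it right that splint harms have no place in the anticipated/unanticipated field. The section 3 sentence is limited to the injection and is not worded as exhaustive, and whether a serious device effect was anticipated is judged against a risk analysis report outside these documents. The splint harms are simply not listed there.

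The reply does not remove the gap. Grades 2 to 4 and the ADE definition do not mention procedures. AE descriptions could help afterwards, but no tabulation by component is planned, and a causal judgement not recorded at the time may be hard to reconstruct.

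**Conclusion.** The point holds as a gap in definitions and in what is recorded. Splint-related events can be classified inconsistently between arms because the device terms are undefined and the ADE definition omits the comparator. Separately, where the device is taken as OOT plus splint, as the label in 2.4.2 suggests, one grade merges three sources of harm in the combined arm. The relatedness table then cannot serve its aim of describing the safety of OOT.

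The size is not estimable from the documents. Under Reading A the spurious ADE difference equals the number of splint injuries in the combined arm; under Readings B and C it is zero. The finding affects device-effect classification and the relatedness table. It does not affect overall AE incidence, severity or onset by arm, the sample size, or any efficacy analysis. The change is worth making before AE forms are in use, because relatedness is judged event by event.

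**What to change.** - In 3.1 and 3.2, state which items are the investigational device and the study device, and use those terms throughout.
- Apply the ADE and SADE definitions to the comparator splint as well.
- Replace the single relatedness item with three, each on the existing five-point scale and completed in both arms: OOT, the aspiration/injection procedure, and the splint. In the splint arm the first two would be expected to be 'not related'; the gain there is a splint grade given under the same rule as in the combined arm.
- In 7.5, tabulate relatedness by component and arm.
- In section 3, list the splint harms named in 4.1 beside the anticipated injection-related AEs.

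The cost is two extra items on the AE form (three in place of one), short wording changes in 3, 3.1, 3.2 and 7.5, and slightly more investigator time per AE. A definition alone would settle consistency between arms; the separate grades are what allow OOT-related events to be identified.

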3.2. Adverse Event Assessments

All AEs reported to or identified by investigative center personnel will be assessed by the investigator and recorded in the patient's study chart and on the AE form, including but not limited to the following:

- Observed or volunteered problems
- Physical signs and symptoms
- Medical condition that occurs during the study, having been absent at baseline
- Medical condition present at baseline that appears to worsen during the study

All AEs will be documented on the AE Form regardless of whether the medical/clinical event is associated with the use of the investigational device.

Each AE record must include a description of the event, date of onset, date of resolution (when known), severity, action taken, relationship to study device and seriousness criteria. Each AE must be recorded separately.

An outcome which may be expected to occur following any joint aspiration and injection procedure (e.g. transient pain at the injection site, mild swelling of the joint) should not be classified as an AE unless it is considered to be more severe or of longer duration or otherwise more pronounced than is typical.

Negative responses on follow-up questionnaires, which are intended to evaluate clinical efficacy, will not be recorded as AE. A worsening of index thumb OA (i.e. joint space narrowing observed on X-ray) which is considered by the investigator to be part of the normal progression of the disease will not be recorded as an AE.

The investigator using the following definitions will assess **severity**:

- Mild: aware of sign or symptom, but easily tolerated
- Moderate: discomfort enough to cause interference with usual activity
- Severe: incapacitating, with inability to work or do usual activity

The investigator will assess **relationship to the study device** for each AE using the following definitions:

1. Not related: the relationship to the device or procedures can be excluded when:

- the event is not a known side effect of the product category the device belongs to or of similar devices and procedures;
- the event has no temporal relationship with the use of the investigational device or the procedures;
- the event does not follow a known response pattern to the medical device (if the response pattern is previously known) and is biologically implausible;
- the discontinuation of medical device application or the reduction of the level of activation/exposure - when clinically feasible - and reintroduction of its use (or increase of the level of activation/exposure), do not impact on the event;
- the event involves a body-site or an organ not expected to be affected by the device or procedure;
- the event can be attributed to another cause (e.g. an underlying or concurrent illness/clinical condition, an effect of another device, drug, treatment or other risk factors);
- the event does not depend on a false result given by the investigational device used for diagnosis, when applicable;
- harms to the subject are not clearly due to use error;

In order to establish the non-relatedness, not all the criteria listed above might be met at the same time, depending on the type of device/procedures and the event.

2. Unlikely: the relationship with the use of the device seems not relevant and/or the event can be reasonably explained by another cause, but additional information may need to be obtained.
3. Possible: the relationship with the use of the investigational device is weak but cannot be ruled out completely. Alternative causes are also possible (e.g. an underlying or concurrent illness/clinical condition or/and an effect of another device, drug or treatment). Cases where relatedness cannot be assessed or no information has been obtained should also be classified as 'possible'.
4. Probable: the relationship with the use of the investigational device seems relevant and/or the event cannot be reasonably explained by another cause, but additional information may need to be obtained.
5. Related: the event is associated with the investigational device beyond reasonable doubt when:
the event is a known side effect of the product category the device belongs to or of similar devices and procedures;
 - the event has a temporal relationship with investigational device use/application or procedures;
 - the event involves a body-site or organ that
 - the investigational device or procedures are applied to;
 - the investigational device or procedures have an effect on;
 - the event follows a known response pattern to the medical device (if the response pattern is previously known);
 - the discontinuation of medical device application (or reduction of the level of activation/exposure) and reintroduction of its use (or increase of the level of activation/exposure), impact on the serious event (when clinically feasible);
 - other possible causes (e.g. an underlying or concurrent illness/clinical condition or/and an effect of another device, drug or treatment) have been adequately ruled out;
 - harm to the subject is due to error in use;
 - the event depends on a false result given by the investigational device used for diagnosis, when applicable;

- In order to establish the relatedness, not all the criteria listed above might be met at the same time, depending on the type of device/procedures and the event.

Seriousness: If the AE meets any of the SAE criteria mentioned in section 4.1 it is regarded as serious.

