2.4.4. Injection Procedure

Administer the contents of the syringe as a single injection into the joint. The procedure for the injection involves the following steps:

1. Clean the injection area with an antiseptic solution.
2. Apply a local anesthetic on the injection site (optional). If local anesthetic is used, then a topical anesthetic, such as ethyl chloride, is recommended. Under no circumstances may the anesthetic be injected intra-articularly.
3. Position needle into the intra-articular space and confirm needle placement with an ultrasound image (if ultrasound guidance is being used).

4. Attach an empty syringe to the needle, aspirate all available joint fluid (aspiration volume must be recorded).
5. Transfer the syringe that contains the injection solution to the needle positioned at the injection site.
6. Inject all contents of the syringe into the synovial space of the joint. (Take care not to inject extra-articularly or into the synovial tissues and capsule).

A clear ultrasound image is to be taken to document needle placement in the synovial space. Any AEs associated with joint aspiration and injection procedure will be recorded. Additionally, any device processing issues will be recorded. Before discharge subjects will be instructed not to exceed their pre-injection physical activity level for 14 days post-injection.

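### Section 3.2 keeps typical injection reactions out of the AE count; as planned this can lower the count only in the ozone arm, and it is not reconciled with Sections 3 and 3.1

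*Combined protocol and SAP*

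**What the plan says.** Section 3.2 (Adverse Event Assessments) states that a foreseeable outcome of aspirating and injecting a joint "should not be classified as an AE unless it is considered to be more severe or of longer duration", with a further allowance for anything else that exceeds the typical. Its examples are "transient pain at the injection site, mild swelling of the joint". It sets no grade or duration for typical, and the investigator makes the assessment.

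Section 2.4.2 defines the arms as "Subject device: OOT plus thumb splint" and "Comparator device: thumb splint". Section 1.7 gives two ozone injections, and Appendix A schedules them weekly for two weeks. No sham aspiration or injection is described for the splint arm. Section 4.1 names discomfort as a risk of splinting, but Section 3.2 has no exclusion for it.

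Other passages on the same events:

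- Section 3, opening text: "Anticipated AEs associated with the injection procedure include worsening of hand pain and/or function, effusion, and infection". No degree is attached.
- Section 3.1: the AE definition covers events arising from study procedures, and a pre-existing event becomes reportable when its severity or intensity changes. The adverse device effect examples include thumb joint effusion without a threshold, and injection-site reaction only when atypical in degree.
- Section 2.4.4: "Any AEs associated with joint aspiration and injection procedure will be recorded".
- Section 7.5: "descriptive statistics including AE incidence overall and per subject, AE severity, AE device relatedness, and AE onset for each treatment group". AEs are also to describe the safety of a repeat ozone injection.

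**The concern.** An AE rule that can apply to one arm only changes that arm's count and leaves the other alone. Here it filters out mild local reactions to the component that distinguishes the arms. The filter depends on one person's view of what is typical. The plan describes no blinding of that investigator, and without a sham it is plain who was injected. Two investigators could classify the same reaction differently.

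At stake is the safety description, not the DASH analysis. Section 7.5 tabulates AEs by arm and uses them to describe a second injection, and the filtered events bear directly on local tolerability. Section 1.2 says that the best concentration, volume, number and spacing of injections are unclear, so information on local tolerability is worth keeping.

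**Working it through.** The plan gives no reaction rate, so there is no plan figure to reproduce on this point. The sample size rests on DASH and has no bearing here.

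**1. Which arm the rule can reach.** Inputs: 20 patients per arm (Sections 4.4.1 and 7.1); two injections per ozone patient (Section 1.7, Appendix A); none planned in the splint arm (Section 2.4.2).

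- Ozone plus splint: 20 × 2 = 40 planned injections.
- Splint only: 20 × 0 = 0.

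**2. Illustrative size.** Let p be the share of injections followed by a mild local reaction (assumed) and s the share of those judged typical. Unrecorded events = 40 × p × s. With s = 1, the upper bound:

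| Assumed p | Ozone arm | Splint arm |
|---|---|---|
| 10% | 40 × 0.10 = 4 | 0 |
| 30% | 40 × 0.30 = 12 | 0 |
| 50% | 40 × 0.50 = 20 | 0 |

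These are events, not patients. Converting them would need the correlation between a patient's two injections, which the documents do not give.

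**3. The passages side by side.**

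| Event | Section 3.2 exclusion | Elsewhere |
|---|---|---|
| Brief rise in thumb pain after injection, in a thumb already painful at entry (Section 2.1) | Can be left out as typical | Section 3.1: a pre-existing event that changes in severity or intensity is reportable. Section 3.2 itself also lists baseline conditions that worsen |
| Mild joint swelling or effusion | Swelling left out unless beyond typical | Sections 3 and 3.1: effusion listed without a threshold |
| Mild procedure-related event | Can be left out as typical | Section 3.1: procedure-related events are included. Section 3.2 has a Mild grade for symptoms that are noticed but easily borne |
| Injection-site reaction | Left out unless beyond typical | Section 3.1: same limit, so consistent |

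**4. Whether another measure would show these reactions.** In the injection column of Appendix A, VAS is taken before the procedure. The first follow-up is at 1 month (Section 2.4.6), and VAS covers only the preceding 48 hours (Section 2.6.4). Section 3.2 also bars poor questionnaire answers from being recorded as AEs. A reaction lasting a few days may leave no clear trace.

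**The case against.** The strongest reply is that this is an openly stated degree threshold. Reactions that are more severe, longer or more marked than typical remain AEs, infection is untouched, and serious events are still captured. The injection-site-reaction example in Section 3.1 uses the same limit. Section 7.5 is descriptive, with no between-arm safety test and no safety endpoint. All of this stands and limits the point.

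A reader might infer several stronger things that the documents do not support:

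- *That all injection reactions are ruled out.* Only those judged typical are.
- *That Section 3.2 contradicts the anticipated-AE list outright.* That list can be read as naming kinds of event that are anticipated once they qualify as AEs. The firmer problem is the unreconciled overlap on effusion and on change in severity.
- *That Section 2.4.4 requires every reaction to be recorded.* It uses the defined term AE, so it inherits whatever threshold Section 3.2 sets.
- *That the commonest harms of ozone injection go missing.* Section 4.1 lists procedure risks without frequencies.
- *That an upper confidence limit on a low AE count would be refuted by the assumed share of patients with any reaction.* The first concerns AEs as defined and the second concerns any reaction, so they are different quantities.

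Section 2.5.3 mentions cross-over, so a splint patient might in principle be injected. No cross-over procedure is described, so the statement that only one arm is affected holds for the arms as planned.

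**Conclusion.** The point holds in limited form. Under the planned arms, the exclusion can lower the AE count only in the ozone arm, it turns on an undefined standard, and it is not reconciled with Sections 3 and 3.1. The by-arm AE table and the repeat-injection summary will understate mild local reactions to injection to the extent that reactions are judged typical. Capture of serious, prolonged or atypical events is not in question.

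The direction follows from the design: 40 planned injections against 0. The size is not known from the documents. The range of about 4 to 20 unrecorded events rests on assumed rates of 10% to 50% per injection, on every ozone patient receiving both injections, and on every reaction being judged typical. It is an illustration, not an estimate. The change is worth making because it is cheap and removes a one-directional undercount.

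**What to change.** 1. Reconcile Sections 3, 3.1 and 3.2 so that post-injection pain, swelling and effusion are treated alike in the definition, the anticipated list and the assessment rules.
2. Record every local reaction after aspiration or injection on the existing AE form with severity, onset and duration, flagged as an expected procedure reaction. Use the AE collection points already in Appendix A: the injection visits and 1, 3 and 6 months.
3. Ask splint-only patients the same index-thumb pain and swelling items at their scheduled contacts.
4. In Section 7.5, tabulate AEs by arm with and without the flagged reactions, so that the sponsor keeps its distinction and readers see the full burden.

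Defining typical by grade and duration would remove the ambiguity, but by itself would leave the one-directional undercount.

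The cost is one flag and a few items on existing forms, with no new visits. More mild AEs will appear in the ozone arm, and some reactions after the second injection will rely on recall at 1 month. A checklist needing extra post-injection contacts or a diary would reduce that recall problem, but it is a larger burden and is not needed for this point.
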